| THA | Total Hip Arthroplasty |

| | | |
|---|---|---------------------------------------|
|  Document No. 2019-10-EVLR-N | SAGITTA EVL-R STEMS – NOVAE / SAGITTA EVL-R CUPS | ID RCB : 2019-A01777-50 |
| | Version 02 | Page No. Page 10 sur 28 |

2 Rational of the study

The prevalence of total hip U.S. population was 0.83% with an estimated 2.5 million patients treated surgically (1.4 million women and 1.1 million men) in 2010 (Maradit Kremers et al. 2015). In France, there were 111000 procedures in 2012 with an increasing tendency (FOUTEAU 2014). Considering the ageing of the population involving an increasing proportion of pathologies, these surgical procedures are among the most common performed surgical treatments. Moreover, there's tendency of a shift to younger ages, probably due to lifestyles. This public health state must be managed to avoid complications as much as impossible to reduce postoperative costs by applying well codified surgical procedures. So, choices of adequate devices and surgical strategies are essential these hip pathologies.

Total Hip arthroplasties are most preferred to treat coxopathies (Primary or secondary osteoarthritis, osteonecrosis, but not limited to) and fractures of the femoral cervix (FOUTEAU 2014).

To be in accordance with the Medical Devices Directive (93/42 CE) and to the future Medical Devices Regulations (2017/745), SERF must monitor their devices by mounting post-market clinical follow-up (PMCF) investigations. This PMCF study aims to improve the knowledge on the performance, the safety and the benefit/risk ratio of Sagitta EVL-R stems prosthesis and to consolidate the strategy of care for patients through this clinical evaluation. The experience of the investigator is also to be underline considering his historic patient population and results already published (Teyssédou et al. 2013). Thus, good significant clinical results as well as the safety are to be refined with a cohort of patient.

3 Pathology

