For acute pathologies such as fractures, the treatment is surgical with total hip replacement as mentioned in recommendations (AAOS and NICE) (Brown 2017; « NICE - 2017 - Hip fracture management Guidance and guidelines.pdf » 2017).

Considering principal method of surgical strategies, risk factors appear for revision procedure. Moerman et al. have studied the Dutch arthroplasty registry. They have found a revision rate in hemiarthroplasty (HA) of 1.6% at 1 year and 2.5% at 5 years postoperatively. In total Hip Arthroplasty (THA), the rate was 2.4% at 1 year and

| | | | |
|---|------------------------------|---|--------------------------------|
|  | Document No. | SAGITTA EVL-R STEMS – NOVAE / SAGITTA EVL-R CUPS | ID RCB : 2019-A01777-50 |
| | 2019-10-EVLR-N Version 02 | | Page No. Page 11 sur 28 |

4.3% at 5 years postoperatively (Moerman et al. 2018). They have also analyzed that risk factors for hemiarthroplasty were male sex, age below 80 years, a posterolateral approach and uncemented fixation. Risk factors following THA were exactly the same with smoking in addition. To be noted that the age as a risk factor for revision is not a risk factor for revision in the first year after the fracture but becomes one in the years thereafter (Moerman et al. 2018). Whatever the primary or the revision uses, these stems are used mainly due to the encountered pathologies and the need for the supplemental fixations with distal screws.

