6 STUDY OBJECTIVES

The use of femoral stems without cement is known to give long terms satisfying clinical results. In these cases, the sagitta EVL-R stems are especially used for severe traumas of the femur and mainly for revision of arthroplasties for any reason whatsoever, respecting indications of the IFU. The extended and osseointegration of these implants were reported in numerous series, despite the use of stems with many different shapes a, macrostructures, coating repartition materials differences and with or without potentially with additional fixation. This study is attempting to provide further clinical data on this medical device for the post market clinical follow up. It will implement the knowledge of this device concerning its performance and its safety according to the directive 93/42/EEC. The results of this study will be used for marketing supports, conference papers and/or scientific article if possible, and as a basis for claimed current indications for the device.

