13.2 Statistical analysis

The data will be analyzed using an excel Microsoft office 2016. All data will be expressed qualitatively and/or quantitatively (frequency and/or percentage). All data will finally be compared to those found in the bibliography.

The previous section includes the main elements of the statistical analysis plan. This plan may be revised to reflect any modifications to the protocol. Any such revisions will be made before freezing the database.

Statistical analysis will be performed in SERF's facilities.

14 Quality assurance

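### Section 13.2 compares all results with the literature, with no rule for choosing comparators and no split between primary and revision surgery, so the conclusion will depend partly on case mix and on the source picked

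*Protocol*

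**What the plan says.** Section 13.2 plans frequencies and percentages produced in a spreadsheet, then states: "All data will finally be compared to those found in the bibliography". It names no reference study, reference value, selection rule, stratum or interval. It adds: "The previous section includes the main elements of the statistical analysis plan".

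The Summary (Study population) admits both primary total hip arthroplasty and revision of a hemiarthroplasty or total hip arthroplasty. The share of each is not given. Section 6 describes the stem as "especially used for severe traumas of the femur and mainly for revision of arthroplasties".

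The only implant failure rates in the visible text are registry figures in Section 3.1: a "revision rate in hemiarthroplasty (HA) of 1.6% at 1 year and 2.5% at 5 years postoperatively", and for total hip arthroplasty 2.4% at 1 year and "4.3% at 5 years postoperatively". They follow directly on the text about fracture treatment. The same paragraph says that age "is not a risk factor for revision in the first year after the fracture".

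Section 2 supports the investigator's experience by pointing to "his historic patient population and results already published". Section 16.1 says the results will serve mainly as evidence of performance and safety in the claimed indications.

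**The concern.** The study has no control group, performance goal, margin or reference value, and Sections 1 and 8.1 call the sample size arbitrary. The literature comparison is therefore the only step that can turn descriptive percentages into the evidence that Section 16.1 wants.

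Two things are left open at that step. First, nothing separates primary or fracture cases from revision cases. If the two fail at different rates, an overall figure set against a source with another mix measures the mix as well as the stem. Second, nothing says which source is used for which outcome. The comparator can then be settled once the results are known, and one observed rate can be described as better, similar or worse.

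The primary endpoint is exposed too. Table 1 (Section 10) schedules the Oxford Hip Score only at the phone call, so there is no preoperative value to compare with, and the visible text gives no reference score.

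**Working it through.** There is no calculation in the plan to reproduce: 120 is declared arbitrary, without alpha, power or benchmark. The check asks how far the conclusion can move.

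**Inputs from the protocol.** n = 120 (Section 8.1); 5-year revision rates of 2.5% and 4.3% (Section 3.1).

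**Assumptions.** All 120 patients are followed to 5 years. Revision cases are 50% to 70% of the cohort and fail at 5% to 15%; all other cases fail at 4.3%. The protocol gives neither the revision share nor a failure rate for revision surgery.

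**1. Dependence on the comparator.** Expected failures are 120 × 0.025 = 3.0 and 120 × 0.043 = 5.16. Take 8 observed failures: 8/120 = 6.7%, exact (Clopper-Pearson) 95% CI 2.9% to 12.7%.

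| Comparator | Relation to the interval | Reading |
|---|---|---|
| 2.5% (Section 3.1) | below it | worse |
| 4.3% (Section 3.1) | inside | compatible |
| 10% (assumed) | inside | compatible |
| 15% (assumed) | above it | better |

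A smaller count does not show this. With 4/120 = 3.3% (CI 0.9% to 8.3%), the point estimate falls between 2.5% and 4.3%, but the interval covers both. That example shows only that bare percentages, which are all Section 13.2 plans, can suggest a difference the data do not support.

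**2. Case mix alone.** With revision share s and revision-case failure rate q, expected failures = 120 × [s·q + (1 − s) × 0.043]. The ratio is to 5.16.

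| s | q | Overall rate | Expected failures | Ratio |
|---|---|---|---|---|
| 50% | 5% | 4.65% | 5.6 | 1.1 |
| 50% | 10% | 7.15% | 8.6 | 1.7 |
| 50% | 15% | 9.65% | 11.6 | 2.2 |
| 70% | 5% | 4.79% | 5.7 | 1.1 |
| 70% | 10% | 8.29% | 9.9 | 1.9 |
| 70% | 15% | 11.79% | 14.1 | 2.7 |

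In every row the stem performs exactly as expected within each stratum.

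**3. How often this would look like a device problem.** Against 4.3%, 11 or more failures in 120 would look worse (one-sided exact p = 0.015). At 70% revisions the chance of reaching 11 is 3%, 41% or 85% for q = 5%, 10% or 15%. At 50% revisions it is 2%, 24% or 62%.

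**4. The bias can run the other way.** Against a source made up only of revisions with a rate of 15%, 120 × 0.15 = 18 failures are expected. The mixed cohort with 50% revisions at that same rate expects 11.6, a ratio of 11.6/18 = 0.64. The stem would look favourable only because of the primary cases.

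**The case against.** Several points on the other side are sound.

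- **The registry is not named as the comparator.** Its rates stand in a background section and introduce risk factors. A reader might infer that a mainly revision cohort will be judged against fracture patients; no sentence says so. That the registry population is fracture patients is itself read from context.
- **The bibliography may be a fixed list.** The contents page shows a Section 18 with that title, which is not in the text available here. If that list is meant, the sources were set in advance. Even so, Section 13.2 does not say which of them applies to which outcome or type of patient.
- **Better-matched literature may exist.** The Summary refers to reviewed literature on an equivalent device in a similar population. It gives no rates and is not tied to Section 13.2.
- **The investigator's own series.** A reader might infer from Section 2 that it will be a benchmark, and that it shares patients with this single-centre cohort operated between 2011 and 2014. The protocol cites it to show experience. It does not say that it used this stem or will be a comparator, and overlap cannot be shown.
- **Pooling is not stated.** It is implied by silence. Operative indication (Section 10.1) and type of intervention (Section 12.3) are recorded, so a split is feasible.
- **Failure rates are secondary, and detail may sit in a separate analysis plan.** The Oxford Hip Score nevertheless relies on the same comparison, and Section 13.2 presents the protocol as already holding the plan's main elements.

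These points limit the claim. They do not supply a comparator rule or a split by procedure.

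**Conclusion.** The concern holds as a defect in what Section 13.2 fixes: a final comparison of everything with the literature, with no comparator rule and no separation of primary from revision surgery, in a cohort that contains both.

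Under the stated assumptions, case mix alone gives about 5.6 to 14.1 expected failures in 120 against 5.2 at 4.3%, a ratio of about 1.1 to 2.7. The lower end is negligible; the upper end would pass for a device problem. Separately, 8/120 reads as worse, compatible or better as the reference moves from 2.5% through 4.3% to 15%. The 15%, the revision share and the revision-case rates are assumptions.

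A ratio as high as 3.5 (15%/4.3%) would need every patient to be a revision case, which the Summary rules out by admitting primary cases. The documents also do not establish that a mismatched benchmark has been chosen, or that the error would favour the device. The collected data remain usable; it is their interpretation that is unprotected.

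**What to change.** Rewrite the comparison sentence in Section 13.2 so that:

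- comparator sources for each outcome, including the Oxford Hip Score, are listed before the data harvest, or at the latest before database lock, by fixed rules on procedure type, outcome definition and follow-up time;
- primary/fracture cases and revision cases are reported separately, with confidence intervals;
- each stratum is compared only with a like population, and if no suitable source exists for a stratum, that is stated and the result stays descriptive;
- the investigator's own series, if used, is shown separately and labelled as not independent.

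Section 13.2 already allows revision before the database is frozen, and the variables needed for the split are collected. The cost is a short literature table, smaller strata with wider intervals, and the loss of any choice of comparator after the results are known.

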14.1 Data quality control

The clinical research associate of the sponsor is responsible for monitoring the harvested database, using a sampling manner to verify only specific and the most important data, according to the study control procedure and the monitoring plan of the study. He will check the accuracy and completeness of CRF. The CRA mandated by the sponsor will have a direct access to the source documents (hospital record and other document related to the study for each patient of the study).

The presence, likelihood and coherence of the data will be controlled in the database. Queries will be edited when corrections are detected and needed.

14.2 Monitoring – On site visits

One or two visits will be performed considering that the harvest will be made only once during ~~2 to 4~~ 8 to 10 days. These visits will be performed either by a person suitably qualified and appointed by the Sponsor, either at distance.

The monitoring visit will be made by mandated Clinical Research Associates under the Sponsor responsibility. The Investigator and staff members agree to be available during the quality control visit. This visit will be programmed once. Following items will be checked:

- Compliance to the protocol and its procedures;
- Quality of data recorded in the CRF: accuracy, missing data, consistency with source data;
- Reporting of serious adverse events.

The investigator must maintain a comprehensive and centralized filing system (investigator site folder) of all study-related documentation that is suitable for inspection by sponsor's monitor or representatives of other regulatory agencies.

15 Ethics and regulatory aspects

15.1 Information to patients

The patient is contacted by a phone call. The study will be explained, and all the points of the information note will be raised. The patient will have a judged adequate and sufficient time in order to take its own decision for its participation in the study. The patient gives orally its agreement to be included in the study, or to refuse it. If he accepts and does not object to the collection of the data, the questionnaire can then begin. The information notice can be sent after the phone call.

All other requirements suggested by the General Data Protection Regulation (GDPR) are presented the information sheet.

This study has received a favorable opinion from the ethical committee.

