| Study visits | 
There's no inclusion period because of the retro-prospective design of the study. Only a phone call will be performed following the start of the data collection. The data collection would be performed during 2 to 4 8 to 10 consecutive days, depending of the ease to consult patient files.
 
Duration of the follow-up period for each patient: until a maximum of 8 years postoperatively. In fact, operated patients between 2011 and 2014 in a single center will be potentially eligible. Therefore, the maximum follow-up through a phone call will be between 5 to 8 years.
 
Patients will be followed at 2 stages: through their medical files (pre-operative, per-operative, immediate post-operative and postoperative follow-up), and between 5 to 8 years after implantation through a single phone call.
 |
| Study population | 
Constitution and follow-up of a cohort of patients operated for a primary total hip arthroplasty or a revision of hemiarthroplasty or total hip arthroplasty with implantation of
 |

the sagitta EVL-R femoral stem at a minimum. Most of time, several implants of the assembly are changed in case of revision. In case of primary surgical intervention, a stem + head and intermediate cup will be implanted for hemiarthroplasty; and a stem + head + insert + cup will be implanted for a total hip arthroplasty.

Inclusion criteria:

- Patients over 18 years old.
- Patients that were treated with the sagitta EVL-R stem for an indication of arthroplasty and according to the Instruction For Use (IFU).
 - Primary or secondary arthrosis,
 - Advanced joint destruction resulting from rheumatoid arthritis or traumatic arthritis,
 - A fracture or an avascular necrosis,
 - Following a previous surgical operation, on condition that the new device does not interfere with the material in place.
 - indicated in the case of primary or secondary arthrosis, displaced sub-capital or transcervical fracture as well as stages I and IIB bone loss according to the PAPROWSKI classification.
 - The SAGITTA EVOLUTION for REVISION implant is recommended for indications according to the bone loss classifications of SOFCOT stages I to VI, PAPROSKY types I to VI and the AAOS types Ia to Ic.
 - Dysplasia
- Patient being informed to the study and non-opposed of its participation and the use its pertaining data.
- Patients with a minimum follow up of 24 months.

Non-inclusion criteria:

- Patient presenting a contraindication indicated in the IFU.

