6.4 Secondary endpoints

The endpoints are:

- The functional improvement following a total hip arthroplasty will be evaluated postoperatively at the

| | | |
|---|---|---------------------------------------|
|  Document No. 2019-10-EVLR-N | SAGITTA EVL-R STEMS – NOVAE / SAGITTA EVL-R CUPS | ID RCB : 2019-A01777-50 |
| | Version 02 | Page No. Page 17 sur 28 |

last follow -up between 5 and 8 years postoperative years through the validated Oxford Hip Score

- The daily physical activity will be appreciated postoperatively at the last follow-up postoperatively.
- The co-morbidity will be measured preoperatively and postoperatively at 6 months, 1, 2, 5, and potentially between 5 to 8 years postoperatively.
- The global satisfaction of patients will be measured at the last follow -up between 5 and 8 years postoperative years.
- The walking ability will be measured at the last follow-up between 5 and 8 years postoperative years.
- The global functional improvement will be measured at the last follow-up between 5 and 8 years postoperatively.
- The pain release will be estimated at the last follow-up between 5 and 8 years postoperatively.
- The length of the operated limb will be harvested at 6 months, 1, 2, 5 and/or at 5 to 8 years postoperatively, if available.
- Adverse events all along the postoperative follow-up and if the information is available in patients' files:
 - Nature and origins of complications.
 - graded as serious (leading to death, life-threatening condition, requiring hospitalization or lengthening of hospital stay, leading to permanent or significant disability);
 - or graded as not serious and as implant-related (migration, subsidence) or surgery-related (iatrogenic event) or other relationships (i.e. aseptic loosening...), idiopathic events, possible related pathology events, but not limited to.

6.5 Secondary radiographic outcomes:

Postoperative Radiological assessments will be followed at immediate postoperative period and at 6 months, 1, 2, 5, and potentially between 5 to 8 years postoperatively. The inclination of the cup, the localization of the center of rotation, and the presence or not of a periprosthetic radiolucent line will be followed and its location. Moreover, the distance, the height of the stem comparing with an anatomic locator (greater or lesser trochanter) and the presence or not of a periprosthetic radiolucent line all around and its location.

7 Study design

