8.2 Inclusion criteria

The inclusion and exclusion criteria are controlling legal aspects of a clinical study in general; and the respect of indications cited in the instruction for use of the medical device. There's no other imposed restrictions.

The inclusion criteria are:

- Patients over 18 years old.
- Patients that were treated for an indication of arthroplasty and according to the Instruction For Use (IFU).
 - Primary or secondary arthrosis,
 - Advanced joint destruction resulting from rheumatoid arthritis or traumatic arthritis,
 - A fracture or an avascular necrosis,
 - Following a previous surgical operation, on condition that the new device does not interfere with the material in place.
 - indicated in the case of primary or secondary arthrosis, displaced sub-capital or transcervical fracture as well as stages I and IIB bone loss according to the PAPROWSKI classification.
 - The SAGITTA EVOLUTION for REVISION implant is recommended for indications according to the bone loss classifications of SOFCOT stages I to VI, PAPROSKY types I to VI and the AAOS types Ia to Ic.
 - Dysplasia
- Patient being informed to the study and non-opposed of its participation and the use its pertaining data.
- Patients with a minimum follow up of 24 months.

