8.4 Definitive inclusion

A patient is definitely included in the study if declared eligible during the electronic file assessment.

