8.5 Exclusion criteria

After inclusion, patients can be excluded from the study if the final follow up is 24 months and if available data at the 24 months postoperative visit is too poor.

9 Study procedures

Patient information:

This observational study does not require any additional eligibility criteria, any additional exam. According to French regulation, each patient is appropriately informed of his/her freedom to decline or agree to participate to the study (thanks to the information note) and of his rights regarding medical data collection.

Study withdrawal:

Patients may withdraw from the study at any time at their own request, or they may be withdrawn at any time at the discretion of the investigator or sponsor for safety, behavioral, or administrative reasons. In any circumstance, every effort should be made to document patient outcome, if possible.

| | | | | | |
|--|----------------|---|-------------------------|----------------|--|
|  serf | Document No. | SAGITTA EVL-R STEMS – NOVAE / SAGITTA EVL-R CUPS | ID RCB : 2019-A01777-50 | | |
| | 2019-10-EVLR-N | | Page No. | Page 19 sur 28 | |

10 Collected data

Patients will be followed at 2 stages: in their medical history files and through a phone call [after](#) the surgery.

| Endpoints | Preoperative | Per-operative | Immediate post-operative | Visit 6 months | Visit 1 year | Visit 2 years | Last visit over 2 years | Phone call to patients |
|--|---|---------------|--------------------------|----------------|--------------|---------------|-------------------------|------------------------|
| Patient information (gender, age, weight, height) | X | | | | | | | |
| Eligibility criteria | X | | | | | | | |
| Medical & surgical history | X | | | | | | | |
| Oxford questionnaires | | | | | | | | X |
| Daily physical activity | | | | | | | | X |
| Charnley Classification | X | | | X | X | X | X | X |
| Surgery - Assembly components description | | X | | | | | | |
| Peroperative Incidents | | X | | | | | | |
| Global results: Patient satisfaction Walking ability Functional improvement Pain release | | | | | | | | X |
| Length of the operated limb | | | | | | | | X |
| Radiologic assessment | Inclinaison of the Cup and localization of the center of rotation | | X | X | X | X | X | X |
| | Periprosthetic radiolucent line - Cup | | X | X | X | X | X | X |
| | Stem height/ anatomic locator | | X | X | X | X | X | X |
| | Periprosthetic radiolucent line - stem | | X | X | X | X | X | X |

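### Sections 8.2 and 15.1 conflict with sections 8.4 and 8.5 on when a patient is included, and the protocol does not say whether patients who died or cannot be reached before the late phone call belong to the safety cohort.

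*Protocol*

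**What the plan says.** **Rules that tie inclusion to the call**

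- Protocol 8.2 lists as a criterion: "Patient being informed to the study and non-opposed of its participation and the use its pertaining data".
- Protocol 15.1 describes how this happens: "The patient is contacted by a phone call", the study is explained, and "The patient gives orally its agreement to be included in the study, or to refuse it". The questionnaire starts after acceptance. The information notice may follow the call.

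**Rules that place inclusion at the file**

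- Protocol 8.4: "A patient is definitely included in the study if declared eligible during the electronic file assessment".
- Protocol 8.5: after inclusion, "patients can be excluded from the study if the final follow up is 24 months", provided that the 24-month data are also too poor.
- Protocol Summary, Study visits: "Only a phone call will be performed following the start of the data collection".

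**What the cohort is used for**

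- Section 8.1 calls it 120 consecutive patients.
- Section 6.2 plans a global survival rate at each timepoint, with aseptic loosening and complication rates. Section 6.5 plans radiographs from the immediate postoperative period onwards.
- Section 6.4 has events "graded as serious (leading to death, life-threatening condition" as part of its definition of serious.
- Section 11.2 collects adverse events from the files and, principally, by questions during the call.

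A further criterion in 8.2 reads "Patients with a minimum follow up of 24 months". The visible text has no rule for patients who have died or cannot be contacted.

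**The concern.** The two sets of rules lead to two different cohorts. Take a patient operated on in 2012 who died in year 4 with a complete surgical, radiographic and complication file. Under 8.4 this patient is in the study. Under 15.1 the patient can neither be informed nor agree, fails the criterion in 8.2, and is left out.

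For the Oxford Hip Score this makes no difference, because the score exists only for people who answer the call. For implant survival, loosening, complications and radiographs it does. Part or all of that information is already in the file. Selecting patients by whether they are alive and reachable years later conditions early results on a late event. Section 3.1 says that femoral neck fractures, which are among the indications, occur more often after 65, so deaths before the call are foreseeable. Section 16.1 intends the results mainly as proof of performance and safety, so readers need to know whom the safety rates describe.

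**Working it through.** **1. When would the call take place?** Surgery ran from 2011 to 2014 (Summary, Study visits) and the study starts in November 2019 (7.3). Potential follow-up runs from about 4.9 years (surgery at the end of 2014) to about 8.9 years (start of 2011). Every called patient therefore has a final contact at roughly 5 years or later.

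**2. What does 8.5 imply?** It describes an included patient whose final follow-up is 24 months. By step 1, such a patient appears to have had no late call. Section 8.5 thus seems to accept inclusion without a call, which 15.1 does not.

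**3. Does 8.4 settle the matter?** Not by itself. It depends on the patient being declared eligible, and eligibility includes being informed and non-opposed (8.2). Section 10.1 has the investigator check the criteria at selection, but a hospital file cannot show that a patient was informed of this study. The conflict remains.

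**4. Can the plan's own figure be reproduced?** No. The cohort size of 120 is called arbitrary (Summary; 8.1), with no allowance for patients who cannot be called. If only patients who agree by phone count and a share d is dead or unreachable, reaching 120 needs 120/(1 − d) eligible files, rounded up: 134 at d = 10%, 150 at 20%, 200 at 40%. The 120 would then not be consecutive.

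**5. How large could the effect be?** The protocol gives no mortality, contact or failure rate for this cohort. As a reference, take the 4.3% five-year revision rate after total hip arthroplasty from the Dutch registry analysis cited in 3.1. In 120 patients this is 120 × 0.043 = 5.2 expected events, so one or two lost events change the rate visibly.

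Let k be the failure rate in unreached patients divided by that in reached patients. Then

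observed rate = true rate / ((1 − d) + k·d).

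Both d and k are assumptions:

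| d | k | Calculation | Observed rate if the true rate is 4.3% |
|---|---|---|---|
| any | 1 | 4.3 / 1 | 4.3% |
| 10% | 2 | 4.3 / 1.1 | 3.9% |
| 20% | 2 | 4.3 / 1.2 | 3.6% |
| 20% | 3 | 4.3 / 1.4 | 3.1% |
| 40% | 3 | 4.3 / 1.8 | 2.4% |

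If k is below 1, the denominator is below 1 and the observed rate is too high.

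**6. Bounds without any assumption on k.** For 120 eligible patients, with events among the reached at about 4.3% (rounded), count the unreached first as all free of failure and then as all failed:

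| d | Reached | Events | Observed | Lowest | Highest |
|---|---|---|---|---|---|
| 10% | 108 | 5 | 4.6% | 5/120 = 4.2% | 17/120 = 14.2% |
| 20% | 96 | 4 | 4.2% | 4/120 = 3.3% | 28/120 = 23.3% |
| 40% | 72 | 3 | 4.2% | 3/120 = 2.5% | 51/120 = 42.5% |

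The upper bounds are extreme. They show only how little the reached patients alone establish about the full cohort.

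**The case against.** The strongest reply is that the protocol already includes patients from the file. Section 8.4 says so, 8.5 presupposes it, and the Summary places the call after data collection has begun. The agreement in 15.1 might be meant to open the questionnaire, and section 9 mentions an information note, so the call need not be the only route. The note itself is not visible here. This stands as a possible reading, but 15.1 speaks of agreement to inclusion in the study, so the wording does not secure it.

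Three stronger readings are tempting and should not be drawn:

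- **That the safety rates describe late survivors only and that fatal events are zero by construction.** This follows only if 15.1 is applied. Sections 8.4 and 8.5 allow the opposite.
- **That the bias favours the device.** It is plausible that unreached patients fail more often, but the documents do not show it. Section 3.1 reports age below 80 as a risk factor for revision, so older fracture patients who die may have a lower risk, and death shortens the time at risk. Male sex, and smoking after total hip arthroplasty, are also listed there and could act the other way.
- **That complications come from the files alone and do not need the call.** Section 11.2 relies principally on the call for adverse events. Uncalled patients can be kept, but with less complete information.

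**Conclusion.** The protocol contradicts itself on the point of inclusion and leaves the dead and unreachable undefined. That much rests on its text alone. The consequence is conditional: if a site follows 15.1, eligible patients with documented follow-up are lost, the cohort is not consecutive, safety and radiographic results are conditioned on being alive and reachable, and deaths before the call cannot be counted.

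Neither the direction nor the size of the bias in device-failure rates can be taken from the documents. The fall from 4.3% to between 3.9% and 2.4% rests on the assumed non-contact shares of 10% to 40% and failure ratios of 2 to 3, with the registry rate borrowed as a reference. It disappears at a ratio of 1.

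The 24-month minimum follow-up in 8.2 separately removes earlier deaths and losses. Resolving the call question therefore does not by itself give an unselected cohort.

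**What to change.** Reconcile 8.2, 8.4, 8.5 and 15.1 as follows:

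- **File-based outcomes** (implant survival, loosening, complications on file, radiographs): use all consecutive eligible patients who have not objected. Include the deceased and the unreachable as far as the ethics committee and the non-opposition rules allow. End follow-up at death or last documented contact.
- **Living patients who cannot be reached by phone:** send the existing information note by post, with a period in which to object.
- **Call-collected items** (Oxford Hip Score, daily activity, global results, adverse events reported by phone): keep agreement at the call as the condition.
- **Reporting:** give the numbers implanted, eligible, objecting, dead, unreachable and called.

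The analysis plan can settle how death enters the survival estimate. Who belongs to the cohort should be fixed in the protocol.

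The cost is rewording, an ethics notification and a mailing. There are two downsides: the safety rates may turn out less favourable, and events in uncalled patients will be known only from the hospital file, so treatment elsewhere may be missed. The report should state this, together with the effect of the 24-month criterion.
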